Project number: 2017YFC1700602

**A Multicenter, Double-blind, Randomized, Placebo-
controlled Clinical Trial of Shenbai Granules in
Reducing Recurrence of Colorectal Adenoma**

Sponsor: Affiliated Hospital of Nanjing University of Chinese Medicine

Principal investigator: [name]

Version number: 7.0

Version date: September 16, 2021

Ethical approval number: No.2018NL-067-09

Synopsis.....	3
Study visits flow chart.....	5
1. Background.....	7
2. Study objectives.....	7
3. Study design.....	7
4. Selection of subjects.....	8
5. Intervention.....	10
6. Observation indicators.....	12
7. Adverse events.....	13
8. Quality control and warranty.....	15
9. Data administration.....	16
10. Statistical analysis.....	16
11. Ethics.....	17
12. Summary and data preservation.....	18
13. Task allocation.....	18

Synopsis

Title	A multicenter, double-blind, randomized, placebo-controlled clinical trial of Shenbai Granules in reducing recurrence of colorectal adenoma
Participating units	
 1. Affiliated Hospital of Nanjing University of Chinese Medicine 2. Guangdong Provincial Hospital of Traditional Chinese Medicine 3. Longhua Hospital Affiliated to Shanghai University of Traditional Chinese Medicine 4. Shuguang Hospital Affiliated to Shanghai University of Traditional Chinese Medicine 5. the First Affiliated Hospital of Guangzhou University of Traditional Chinese Medicine 6. Affiliated Hospital of Naval Military Medical University 7. Beijing Friendship Hospital, Capital Medical University 8. the First Affiliated Hospital of Nanjing Medical University 9. Chinese Evidence-Based Medicine Center, West China Hospital, Sichuan University
Purpose	
 1. To evaluate the efficacy and safety of Shenbai Granules in reducing recurrence of colorectal adenoma 2. To provide high-quality, internationally recognized, evidence-based medical evidence for the clinical guidelines of traditional Chinese medicine in the prevention and treatment of colorectal adenoma
Design	Prospective, multicenter, double-blind, randomized, placebo-controlled clinical trial
Sample size	Total 400: Shenbai Granules group, 200; Placebo group, 200
Test Population	Patients aged 18-70 years who have undergone complete polypectomy within the recent 6 months and pathologically confirmed colorectal adenomatous polyps

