Colorectal cancer (CRC) is one of the most common malignant tumors that threaten human health, and its morbidity and mortality are increasing year by year. Colorectal adenoma (CRA) is the precancerous lesion of CRC. Endoscopy has become an important treatment for CRA. But endoscopic polypectomy does not reduce the recurrence and cancerization rate of adenoma. At present, measures such as increasing dietary fiber, smoking cessation, and appropriate supplementation of calcium and vitamin D are used to prevent the recurrence of CRA. However, there is no established chemopreventive agent for the prevention of recurrent CRA.

With the innovative development of the "preventive treatment for disease" theory of traditional Chinese medicine (TCM), the clinical and mechanism studies on the prevention and treatment of CRC have gradually become a research focus. Under the guidance of [name], a famous TCM master, our research team combined clinical practice to propose "accumulation of dampness and heat, deficiency of spleen and Qi" as the basic pathogenesis of CRA and established the TCM formula "Shenbai Granules (SBG)" (*Sophorae flavescens* radix, *Hedyotis diffusa*, *Codonopsis* radix, *Atractylodes macrocephalae* rhizoma, *Coicis semen*, *Coptidis* rhizoma, *Mume fructus* and *Zingiberis rhizome praeparatum*). The combination of the whole formula has the functions of beneficial Qi, invigorating spleen, clearing heat and dampness. Previous studies have found that Shenbai Granules could significantly reduce the recurrence of CRA and promote the apoptosis of colorectal cancer cells.

Therefore, we plan to conduct a multicenter, randomized, double-blind clinical study to enroll patients diagnosed with adenoma after colonoscopic resection. After obtaining informed consent, the treatment group will receive SBG, and the control group will receive SBG mimic as placebo. The efficacy and safety of SBG will be evaluated by adenoma detection rate (ADR) and adverse events, as well as clinical symptoms. This study aims to provide high-quality, internationally recognized, evidence of evidence-based medicine for the development of clinical guidelines.

2. Study objectives

The primary objective is to evaluate the efficacy and safety of SBG in reducing recurrence of CRA. The secondary objective is to provide high-quality, internationally recognized, evidence-based medical evidence for the clinical guidelines of TCM in the prevention and treatment of CRA.

3. Study design

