3.3 Sample size

According to the literature search and previous research results, the average detection rate of recurrent adenomas without agent intervention for patients after polypectomy is 52%. We hope that ADR will be reduced by 34% after intervention of SBG. With a significance level (alpha) of 5% and power of 90%, the patient number needed is 160 in each group. Allowing for 20% of participants to drop out, the target number of participants to be randomly assigned is 400.

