6.3 Safety indicators

- (1) Physical examination at each visit.
- (2) Laboratory test: Blood routine, urine routine, liver function (alanine aminotransferase, aspartate aminotransferase), renal function (serum creatinine, blood urea nitrogen) will be rechecked before clinical intervention, every visit after taking medicine.
- (3) Adverse events: recording the conditions of adverse events occurring in the whole process from before and after the treatment, and in the observation period.

7. Adverse events

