10.4 Statistical analysis methods

- (1) Descriptive statistical analysis: qualitative indicators are described by frequency table, percentage or constituent ratio. Quantitative indicators are described as mean, standard deviation, or median, lower quartile (Q1), upper quartile (Q3), minimum value, and maximum value.
- (2) Comparative analysis of the two groups: Chi-square test, Fisher's exact test, Wilcoxon rank sum test, CMH χ^2 test, WLS covariance are used for qualitative data. Quantitative data with normal distribution are tested by t test (homogeneity of variance test between groups, 0.05 is used as the test level, Satterthwaite method is used to correct the t test when the variance is not equal). Non-normal distribution is tested by Wilcoxon rank sum test, Wilcoxon signed rank sum test; GLM covariance. Two-sided test is used to test the hypothesis, and the test statistics and their corresponding P values are presented. $P \leq 0.05$ is considered statistically significant, and $P \leq 0.01$ is considered highly statistically significant.

11. Ethics

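### Safety is part of the primary objective, but the protocol text plans only P values for comparing the arms; for uncommon adverse events these cannot show how large a harm has been excluded (minor)

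*Combined protocol and SAP*

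**What the plan says.** Section 2 names two things together: "The primary objective is to evaluate the efficacy and safety of SBG in reducing recurrence of CRA". Section 3.3 works only from adenoma detection, 52% without treatment and a hoped-for reduction of 34%: "With a significance level (alpha) of 5% and power of 90%, the patient number needed is 160 in each group". A 20% dropout allowance brings this to the Synopsis figure: "Total 400: Shenbai Granules group, 200; Placebo group, 200". No power, precision or expected event rate is given for safety.

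Section 6.3 lists physical examination, laboratory tests and adverse events as safety indicators, the last by "recording the conditions of adverse events occurring in the whole process from before and after the treatment, and in the observation period". The Synopsis assigns safety to the safety analysis set (SS), and section 10.2 defines that set. Section 10.3 lists a safety analysis without a method.

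Section 10.4 therefore governs by default, although it never mentions safety. On description it says "qualitative indicators are described by frequency table, percentage or constituent ratio". On comparison it says "Chi-square test, Fisher's exact test, Wilcoxon rank sum test, CMH χ^2 test, WLS covariance are used for qualitative data", and then "Two-sided test is used to test the hypothesis, and the test statistics and their corresponding P values are presented". Significance is judged at 0.05, with 0.01 labelled as highly significant. No section plans a risk difference, a risk ratio or a confidence interval.

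Section 10.1 says that a SAP will be written after the study starts and settled before database lock, and that it will cover methods for the different indicators. The documents do not show its content.

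**The concern.** For adverse events and laboratory abnormalities, the text offers two percentages and a P value. A difference test asks whether the data are incompatible with no difference. The safety question is how large an excess remains compatible with the data, and neither output states that.

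The gap matters most where power is low. A trial sized on an event with a 52% rate has limited ability to detect excesses of events that occur in a few percent. For those, P > 0.05 is a likely result even when the rate has doubled, and a summary line saying there was no significant difference would then carry little information. Sections 2 and 3.3 make this foreseeable at the design stage. The results are meant to inform clinical guidelines on preventive use after adenomas have been removed, so readers will want to know the excess harm that the trial can rule out.

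**Working it through.** **1. The plan's own figure.** Inputs from section 3.3: p1 = 0.52; a 34% relative reduction gives p2 = 0.52 × 0.66 = 0.3432; alpha 0.05 two-sided; power 0.90.

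n = (1.960 + 1.282)² × [0.52 × 0.48 + 0.3432 × 0.6568] / (0.52 − 0.3432)² = 159.7, so 160 per arm. Then 160 / (1 − 0.20) = 200 per arm, 400 in total. The plan's figure reproduces, and no safety quantity enters it.

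**2. Power for an adverse-event doubling.** The control rates are assumptions, because the documents give none. n = 200 per arm is the full randomised number, the largest the SS can be.

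Normal approximation for 5% vs 10%, with mean rate 0.075:

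- Standard error under no difference: √(2 × 0.075 × 0.925 / 200) = 0.02634
- Standard error under the alternative: √(0.05 × 0.95 / 200 + 0.10 × 0.90 / 200) = 0.02622
- Power = Φ[(0.05 − 1.96 × 0.02634) / 0.02622] = Φ(−0.062) = 47.5%, so 52.5% missed

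Exact check: sum the product of the two binomial probabilities over all pairs of counts for which the two-sided 5% test does not reject.

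| Assumed control vs active rate | Missed, chi-square | Missed, Fisher |
|---|---|---|
| 2% vs 4% | 79% | 87% |
| 3% vs 6% | 70% | 77% |
| 5% vs 10% | 53% | 59% |
| 6% vs 12% | 45% | 51% |
| 8% vs 16% | 30% | 35% |
| 10% vs 20% | 19% | 23% |
| 20% vs 40% | under 1% | under 1% |

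The 50% line is crossed close to a control rate of 5% to 6%. By normal approximation, 80% power for 5% vs 10% would need 435 per arm.

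**3. A smaller safety set.** With 160 per arm, 5% vs 10% is missed in 61% (chi-square) or 68% (Fisher). This is a worst case. The SS needs only one dose and some safety data afterwards, and section 4.5 keeps the data of dropouts.

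**4. What an interval would add.** Suppose 20/200 vs 10/200, an exact doubling. Chi-square P = 0.058 and Fisher P = 0.086, both non-significant.

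Wilson limits are 6.57% to 14.94% for 20/200 and 2.74% to 8.96% for 10/200. The Newcombe limits for the difference of 5.0 percentage points are then:

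- Lower: 5.0 − √[(10 − 6.57)² + (8.96 − 5)²] = −0.2
- Upper: 5.0 + √[(14.94 − 10)² + (5 − 2.74)²] = +10.4

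The risk ratio is 2.0 with limits 2.0 × exp(±1.96 × 0.374), or 0.96 to 4.16. The P value says not significant. The interval says that an excess of 10 percentage points, or a fourfold rate, has not been excluded.

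**The case against.** Three stronger readings are tempting, and the documents support none of them.

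- **That the protocol will treat P > 0.05 as proof of safety.** It says no such thing. Section 10.4 is a generic list that does not name safety, and applying it to adverse events is an inference from the lack of any other method. The misreading would be made by a later author or reader.
- **That the trial has no plan for estimating harms.** Section 10.1 sends methods for individual indicators to a SAP that is not shown. One can say only that the protocol text does not commit to intervals.
- **That the trial generally misses a doubling of adverse events.** This depends on the assumed rate. By chi-square the proportion missed is already below half at 6% vs 12%, and 10% vs 20% is detected in about four trials out of five. An overall adverse-event rate over two years could well be in the range where a doubling is found.

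It is also fair to say that low power for uncommon harms is normal in a trial sized on efficacy, and that reporting intervals adds no information to 400 patients. A reader could compute an interval from the published counts. The safety set, severity grading and causality scale are specified, and the lack of effect estimates in section 10.4 is not peculiar to safety.

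These arguments limit the point and lower its weight. They do not remove it. Low power is the reason to report what has been excluded, and leaving the calculation to readers is a poor plan for part of the primary objective.

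**Conclusion.** The point stands in a limited form and is minor. For safety, which shares the primary objective, the protocol text plans percentages and P values but no estimate or interval for the difference between arms. These outputs cannot show how large a harm has been excluded.

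The practical effect is confined to uncommon events. Serious adverse events, discontinuations for adverse events and liver-enzyme elevations may fall in that range. At assumed control rates of 5% or lower, with 200 per arm, a doubling is missed in more than half of trials. At 5% with chi-square the margin over half is narrow, 53%. For commoner events the test mostly detects a doubling.

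The size rests on control rates that are assumed, on the full 200 per arm being in the SS, and on section 10.4 applying to safety by default. The case for intervals does not depend on any particular rate.

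**What to change.** In section 10.4 and the SAP, add a paragraph for safety in the SS:

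- Report the between-arm risk difference with a two-sided 95% confidence interval (Newcombe or Miettinen-Nurminen; exact where events are few) for any adverse event, drug-related adverse event, serious adverse event, adverse event leading to discontinuation, and ALT, AST or creatinine above the upper limit of normal.
- Base the safety statement on the interval, saying what excess in percentage points the upper limit excludes.
- Treat any safety P values as descriptive.
- State that P > 0.05 on a safety comparison is not evidence of safety or of similarity to placebo, because the trial was sized on adenoma detection.

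The cost is a few sentences and some extra table columns. Section 10.1 leaves the SAP open until database lock, and no patients, visits or data are added. The downside is a more cautious safety statement, with wide intervals for rare events.

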11.1 Ethical review

The clinical trial protocol is submitted to the ethics committee for approval before implementation. If the protocol is revised during the implementation of the clinical trial, it needs to be submitted to the ethics committee again for approval. If important new information related to the trial drug is found, the informed consent form have to be revised in writing to the ethics committee for approval, and then the consent is obtained from the subjects again.

This study is reviewed and approved by the Institutional Ethics Committee of the Affiliated Hospital of Nanjing University of Chinese Medicine before the start of the trial. When necessary (such as serious adverse events), the ethics committee should hold a meeting in time for review, and the review conclusion should be reported.

11.2 Benefits and risks

Subjects and society will likely benefit from this research. Such benefits include the potential for improvement in the subject's condition and the possibility that the study could lead to the development of a new treatment that could be used in other patients with similar conditions. Subjects receive free fees for study-related examinations during the study, registration fees at follow-up. Subjects will have access to good medical care for the duration of the study.

11.3 Recruitment of subjects

The relevant information is released through the recruitment notice in the hospital → interested persons sign up → read the study introduction → sign the informed consent form → physical examination → screening → qualified persons sign the informed consent form → selected subjects are randomly divided into two groups. Recruitment notices and study briefs need to be submitted to the ethics committee for review.

11.4 Medical care and protection of subjects

Investigators at the Affiliated Hospital of Nanjing University of Chinese Medicine are responsible for the medical care of the subjects, make relevant medical decisions, and ensure that the subjects receive appropriate treatment in the event of adverse events during the trial.

11.5 Protection of subject privacy

Only investigators and monitors involved in clinical trials may have access to subjects' personal medical records. Data will be processed in a "data anonymization" manner, omitting information that could identify individual subjects.

11.6 The process of informed consent

The detailed information about the clinical trial should be explained, including the purpose of the trial, the trial procedure, the possible benefits and risks, and the rights and obligations of the subjects, etc., so that the subjects can fully understand and have sufficient time to consider, give consent after the questions have been answered satisfactorily, and sign the "informed consent" before starting the clinical trial. When each patient signs the informed consent form, the doctor will give his contact number to the patient, so that the patient can find the doctor at any time if his condition changes.

12. Summary and data preservation

Each research center is equipped with special file cabinets, and special personnel are responsible for keeping and sorting out the trial documents and related data. Special cabinets for trial drugs are set up, and special persons are responsible for drug registration, distribution and recovery. Investigators should submit the study medical records, informed consent forms, and patient medication record cards to the principal investigator of their centers within 3 days after the end of the observation course of each study case. Study data are uploaded to the data management center in accordance with relevant regulations. After the end of the study, all the research data are stored centrally in the project undertaking unit. The study is summarized by the blinded evaluators, and all the original data related to the study are saved by the research group and archived after the conclusion of the project.

13. Task allocation

Randomization is stratified by center, with block randomization. The study is conducted simultaneously in 8 hospitals including the Affiliated Hospital of Nanjing University of Traditional Chinese Medicine (team leader), Beijing Friendship Hospital Affiliated to Capital Medical University, Longhua Hospital Affiliated to Shanghai University of Traditional Chinese Medicine, Guangdong Provincial Hospital of Traditional Chinese Medicine, the First Affiliated Hospital of Nanjing Medical University, Shuguang

Hospital Affiliated to Shanghai University of Traditional Chinese Medicine, Changhai Hospital Affiliated to Naval Medical University, and the First Affiliated Hospital of Guangzhou University of Traditional Chinese Medicine. The random arrangement of 400 subjects to receive treatment is generated by an independent third-party with the help of SAS statistical analysis system. The basic information of the cases is input by each member unit, and the eligible cases are automatically assigned to the treatment group or the control group and received corresponding treatment.

Hospital	Planned number of cases assigned
Affiliated Hospital of Nanjing University of Chinese Medicine	112
Guangdong Provincial Hospital of Traditional Chinese Medicine	84
Longhua Hospital Affiliated to Shanghai University of Traditional Chinese Medicine	52
Shuguang Hospital Affiliated to Shanghai University of Traditional Chinese Medicine	76
the First Affiliated Hospital of Guangzhou University of Traditional Chinese Medicine	48
Affiliated Hospital of Naval Military Medical University	16
Beijing Friendship Hospital, Capital Medical University	8
the First Affiliated Hospital of Nanjing Medical University	4
Total	400
